## VI. Potential Scientific Problems

### Subject drop-out

To account for screen failures and potential 30% dropout, up to 100 subjects may be needed to be recruited to obtain the required 60 subjects. To limit drop-out, we maintain frequent contact with participants, use incentives for visits and adherence, and “surprise” incentives such as sports tickets and raffles to maintain contact with the study team. We find these strategies successful for maintaining compliance in our TODAY study participants. Due to our TODAY and other metformin studies, our staff is experienced with long-term adolescent studies, with excellent study retention for as long as six years. Adverse effects of metformin (nausea, anorexia, diarrhea and vomiting), have been shown to be minimized when the dose is titrated up slowly and taken with meals, and in our blinded study of metformin in obese adolescents, adverse effects did not result in decreased dose or significant patient attrition vs. placebo.

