# **VIII. Data Analysis Plan**

## **A. Data Analysis Plan**

Data analyses and power: For all aims, variables will be checked for the distributional assumption of normality and appropriate transformations applied to normalize the data.

Specific Aim 1a: A placebo-controlled design will be employed using a mixed effect model to determine the effect of treatment and check for the effect of sequence on the effects of metformin to placebo on whole body IR (GIR, mg/kg/min, 1o outcome). Based on the Sarnblad et al article, who had a mean difference of 0.8 and SD of 0.9, with a sample size of 30 per group and an alpha of 0.05, we will have 92% power to detect a difference of 0.8 in the primary outcome of insulin sensitivity. Additional 10 patients will be recruited per/group for a total N = 80 to account for 30% dropout. 100 will be screened to account for screen failures.

Specific Aim 1b: A placebo-controlled design will be employed using a mixed effect model to determine the effect of treatment on the effects of metformin to placebo on ADP t $\frac{1}{2}$  adjusting for baseline mitochondrial function, gender, and Tanner stage. Our preliminary baseline data shows a difference in ADP t $\frac{1}{2}$  between T1D and controls (19.1  $\pm$  0.85 vs. 14.6  $\pm$  0.63, respectively), or an effect size = 5.294. Assuming that T1D patients treated with metformin improve ADP t $\frac{1}{2}$  compared with placebo, we will have > 80% power to detect an effect size as small as 0.645 and a two-sided  $\alpha$  = 0.0125 adjusted for 4 endpoints.

Specific Aim 2a: A placebo-controlled design will be employed using a mixed effect model to determine the effect of treatment on the effects of metformin to placebo on BrachD, adjusting for baseline BrachD, gender, and Tanner stage. Agarwal *et al* demonstrated a mean difference between 3 months of metformin and placebo in young women with PCOS using Aix (-6.1; 95% CI of -8.46-3.74)[93]. If we see a similar effect with common SD = 5.066 calculated from the CI, N = 11 per/group is required for 80% with a two-sided  $\alpha$  = 0.0125 to adjust for 4 endpoints, thus with N = 80 we will have > 99% power for this aim.

Specific Aim 2b: A mixed effect model will be used to compare the effects of metformin to placebo on cardiac dysfunction measured by CS. With N = 80 we will have > 80% power to detect an effect size as small as 0.645 and a two-sided  $\alpha$  = 0.0125 adjusted for 4 endpoints.

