#### Analysis plan:

The primary analysis will be a treatment group comparison of mean change in whole body IR (GIR, mg/kg/min, 1o outcome) obtained at the 3 month visit adjusted for baseline IR, tanner stage, sex, and race/ethnicity in an analysis of covariance (ANCOVA) model.

The primary analysis will follow the intent-to-treat principle. The data of all randomized patients will be included in the analysis regardless of whether the assigned treatment was actually received, according to randomization group.

Multiple imputation using Rubin's method 24 will be used to impute the GIR outcomes that are missing. The primary analysis will be repeated including data from participants with no imputation for missing data. The results will be compared with those using imputation to verify that conclusions are not sensitive to the method for handling missing data.

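### The only planned missing-data check stays within missing at random, so its agreement with the imputed result would not show robustness to informative dropout

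*Combined protocol and SAP*

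**What the plan says.** Under the heading Analysis plan, the primary comparison is change in GIR at 3 months, "adjusted for baseline IR, tanner stage, sex, and race/ethnicity in an analysis of covariance (ANCOVA) model". The intent-to-treat statement reads: "The data of all randomized patients will be included in the analysis regardless of whether the assigned treatment was actually received". For missing values: "Multiple imputation using Rubin's method 24 will be used to impute the GIR outcomes that are missing". The imputation model, its auxiliary variables and the assumed missingness mechanism are not given.

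One check follows: "The primary analysis will be repeated including data from participants with no imputation for missing data". Its purpose is stated as: "The results will be compared with those using imputation to verify that conclusions are not sensitive to the method for handling missing data".

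No delta-adjusted, reference-based, tipping-point or other missing-not-at-random analysis appears in the document. The mixed models described aim by aim in the Data Analysis Plan are not offered as a sensitivity analysis, and they too rest on missing at random.

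On the amount and causes of missing data, section VI (Subject drop-out) sets the recruitment target "To account for screen failures and potential 30% dropout", and the Aim 1a sample-size paragraph uses the same rate. The Visit 4 description and the Subject Discontinuation Criteria withdraw participants who cannot tolerate the minimum dose. The criteria also cover anemia, renal dysfunction, recurrent severe hypoglycemia and lactic acidosis.

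**The concern.** The clamp is scheduled only at Visits 4 and 8 (Table 2), and randomization follows the Visit 4 clamp. What can be missing from the primary analysis is therefore essentially one final GIR per participant. Complete-case ANCOVA is valid if missingness is unrelated to that unseen value given arm and covariates. Standard multiple imputation needs the same condition, given whatever is in the imputation model.

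Two analyses that share an assumption cannot test each other on it. If they agree, the report would be entitled by the plan to say that the conclusion is not sensitive to missing data, when only sensitivity within missing at random has been examined. Some withdrawal routes could be related to treatment and to outcome, so the untested part matters here.

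**Working it through.** **Inputs from the plan (Data Analysis Plan, Aim 1a).** The cited trial is one "who had a mean difference of 0.8 and SD of 0.9" (mg/kg/min); power is computed "with a sample size of 30 per group and an alpha of 0.05"; stated power is 92%; 80 are randomized (40 per arm); dropout is 30%. Two-sided testing is assumed, because Aim 1a does not state it.

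**The plan's own figure.** SE = 0.9 × √(2/30) = 0.232. Power is 93.1% by the normal approximation and 92.3% by the noncentral t with 58 df. The stated 92% reproduces and is not in dispute.

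**Why the two analyses coincide with the same covariates.** Let X_o and X_m be the design rows of participants with and without a final GIR, and b the complete-case estimate. The normal equations give X_o′y_o = X_o′X_o b. Imputed values centre on X_m b. Refitting to the completed data gives, on average over imputations, (X_o′X_o + X_m′X_m)⁻¹(X_o′X_o b + X_m′X_m b) = b. Nothing in this depends on why values are missing.

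**Simulation.** Assumptions: 3,000 trials, 40 per arm, SD 0.9, true effect 0, baseline–outcome correlation 0.5, one baseline covariate and 20 imputations from the same covariates. Placebo loss is 30% at random. In the informative scenario, metformin loss depends on the unseen GIR and averages about 31%.

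| Missingness | Bias, complete case | Bias, imputed | Type I error (complete case / imputed) | Same significance conclusion | Mean absolute difference |
|---|---|---|---|---|---|
| Completely at random | 0.002 | 0.002 | 4.6% / 4.1% | 98.1% | 0.021 |
| Depends on unseen GIR, metformin arm | +0.264 | +0.264 | 25.6% / 24.8% | 95.4% | 0.021 |

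The analyses agree almost as often when both are wrong as when both are right. The size of the bias reflects the assumed dropout slope. The near-identity of the estimates does not.

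**Illustration of size.** Assume a share p of the metformin arm is lost with zero effect, other loss is random, and completers show 0.8. The effect in all randomized is 0.8 × (1 − p), while both analyses report about 0.8.

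- p = 10%: true 0.72, excess 0.08.
- p = 20%: true 0.64, excess 0.16.

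The values of p and the zero effect are assumptions, not figures from the documents.

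**Tipping point.** If missing metformin values are worse than their imputed values by δ and a fraction d is missing, the estimate is 0.8 − dδ. Taking the completers' SE (approximate), significance is lost at δ = (0.8 − 1.96 × SE)/d.

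- d = 30% (28 completers per arm): SE = 0.9 × √(2/28) = 0.241; δ = (0.8 − 0.471)/0.30 = 1.10. If the arms shift equally in opposite directions, the divisor is 0.60 and δ = 0.55 each.
- d = 25% (30 completers per arm, which is what 40 per arm and 60 completers imply): SE = 0.232; δ = (0.8 − 0.455)/0.25 = 1.38, or 0.69 each.

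**The case against.** **The imputation model is not stated.** It could include baseline HbA1c, BMI and insulin dose, or Visit 5 HbA1c, weight, side effects and pill counts. The imputed and complete-case results could then differ. This stands: a reader might infer that the planned comparison is bound to succeed, and the documents do not support that unconditionally. It follows only if imputation uses arm and the ANCOVA covariates. Richer auxiliaries would still leave the analysis within missing at random, and participants withdrawn during the roughly four-week titration would have no Visit 5 data at day 45.

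**Read literally, the sentence concerns the method, and two methods are compared.** That is fair as far as it goes. But it speaks of conclusions not being sensitive, and a comparison within one assumption supports only a narrower statement.

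**The documents point away from large differential loss.** Section III.A.5 reports that blinded metformin was very well tolerated. Section VI reports no significant excess attrition against placebo in the team's blinded study of obese adolescents. The tolerability rule applies to placebo tablets as well. Withdrawal for recurrent severe hypoglycemia could remove strong responders and bias toward the null. All of this stands, so the direction of bias is not known.

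**A reader might infer that informative dropout is the main threat to the primary result.** The documents do not support that. In the zero-effect scenario an ineffective drug yields no bias and so no false positive. At the planned effect, if all 30% missing on metformin had zero effect, the estimate would be 0.8 × 0.70 = 0.56; with SE 0.241, z = 2.33 and p is about 0.02. The tipping shift of 1.10 exceeds the whole planned effect.

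**No analysis of the observed data can detect missing not at random.** Correct. Reference-based and tipping-point analyses show how the result depends on departures; they do not detect them.

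**Conclusion.** The point holds in a limited form. The single planned check cannot support a claim of robustness to informative dropout, because both analyses rest on missing at random. If imputation uses only arm and the ANCOVA covariates, their estimates will nearly coincide (about 0.02 mg/kg/min apart in simulation) whatever the mechanism.

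The possible size is illustrative: 0.08–0.16 too high on 0.8 if 10–20% of the metformin arm were lost with zero effect. It should not be read as an expected bias, since neither the rate nor the zero effect comes from the documents. Likewise, the 25% type I error belongs to one assumed mechanism and is not a forecast for this trial. What the plan does establish is allowance for 30% dropout, withdrawal rules that may relate to treatment, and no analysis outside missing at random. This is a worthwhile, inexpensive improvement to the plan and does not show that the primary result would be wrong.

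**What to change.** Keep multiple imputation as the primary approach and amend the Analysis plan as follows.

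1. State the missing-at-random assumption and the imputation model, including auxiliary variables such as Visit 5 data where available.
2. Pre-specify at least one missing-not-at-random analysis: reference-based imputation of metformin dropouts from the placebo arm, an arm-specific delta-adjusted tipping point, or both. For the tipping point, report the shift at which significance is lost, in mg/kg/min, so that its clinical plausibility can be judged. The 1.10 above is only a planning value and will be smaller if the observed effect is below 0.8.
3. Reword the purpose of the complete-case comparison so that it claims sensitivity within missing at random only.

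The cost is one paragraph and a few extra model runs, with no new data. The downside is that a reference-based estimate may be less favourable than the primary one.

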#### 6.2.2 Secondary Endpoints:

Secondary analyses will include treatment group comparisons of the following:

1. Mean change in hepatic IR
2. Mean change in adipose IR
3. Mean change in ADP t $\frac{1}{2}$  from calf MRI
4. Mean change in BrachD from brachial artery ultrasound
5. Mean change in circumferential strain from echo

#### 6.2.3 Exploratory Analysis:

Correlations between changes in HbA1c and BMI and IR will be assessed.

## **IX. Knowledge to be Gained From This Research**

T1D is increasing among youth. The pediatric incidence in Colorado rose from 14.8/100,000 in 1978-1988 to 23.9 in 2002-2004[196], translating to a lifetime of exposure and risk for early death from CVD [196-201]. Approximately 17 years of life are lost for a child diagnosed with T1D at age 10, a barrier that has not improved over the last four decades [202]. Thus, youth onset T1D creates an especially vulnerable population. Intensive glycemic control is undoubtedly critical to decreasing renal, neurological, and retinal complications, and also correlates with reduced CV mortality [9, 203-205]. However, we currently lack safe or realistic intensive glycemic treatment strategies for youth. As evidence, only 25% of youth in our multi-center T1D EXCHANGE Registry were able to reach HA1c goals, making novel approaches to preventing complications critical[122].

Unaddressed IR may contribute to CVD in T1D, as it does in T2D [17-21, 206]. For example, estimated IR, not glycemia, predicted CVD events and mortality in two adult T1D studies[9, 24], and in our collaborators Coronary Artery Calcification in T1D adults (CACTI) study, clamp-derived IR, not glycemia, predicted CAC[25]. Our previous studies also reveal the presence of IR unrelated to glycemia, along with a dangerous constellation of cardiac, vascular, muscle mitochondrial and exercise dysfunction in normal-weight T1D children, despite short diabetes duration and absence of other typical IR-related co-morbidities. Thus, IR appears to be a common, integral component of T1D pathophysiology, which is not explainable by hyperglycemia or obesity alone. However, the currently increasing rate of obesity in T1D youth[122] is also a critical barrier to progress, as obesity super-imposed on T1D is likely to worsen IR. We propose that controlling IR early in the care of T1D patients may decrease CV morbidity and mortality in this population.

The mechanism of IR in T1D is distinct from T2D as the IR phenotype clearly differs. Differentiating each tissue's response to metformin in T1D, and exploring metformin's impact on the CV system will help direct future therapeutic targets, as will clarifying the relative importance of hyperglycemia vs. IR in the cardiac, vascular, exercise and muscle dysfunction in T1D youth. A 2010 meta-analysis concluded that "properly designed randomized controlled clinical trials of metformin" designed to assess "reductions in CVD in T1D should be conducted forthwith"[60]. Our proposal addresses this significant unmet need. Findings supporting directly treating IR in T1D youth may change the clinical approach to T1D care.

T1D shortens lifespan despite modern advances in control of established CV risk factors[207]. Thus, innovative therapeutic approaches are required if we are to address the excess CVD resulting from T1D. Metformin has been attempted previously in T1D youth, but its limited impact on HbA1c tempered enthusiasm. Few studies have examined the non-glycemic benefits of metformin in T1D. Thus, additional benefits of insulin sensitization or clues to causes of IR in T1D may have been overlooked in the literature. The meta-analysis above determined that metformin significantly reduced insulin dose in T1D, but found no trials that included CV outcomes or their surrogates[60]. Therefore, our proposal is highly innovative in assessing metformin's effects on the CV system in T1D. Our proposal also moves beyond the typical paradigm of approaching IR in T1D as strictly a consequence of obesity. Our preliminary data strongly demonstrate two key novel observations: 1. Both T1D and T2D youth have evidence of mitochondrial, vascular, cardiac and exercise dysfunction that correlates with IR. 2. IR is nearly universal in T1D youth but is not predicted by usual metabolic syndrome features, identifying an entirely unique phenotype. Thus, the mechanism of IR is likely also unique in T1D and may respond differently to therapies than it does in T2D. Our data reframe the traditional model of IR as synonymous with a metabolic syndrome phenotype.

We propose that a new approach of treating or preventing IR in T1D patients at an early age, when defects in CV function may still be reversible, will decrease CVD burden in T1D at later stages of life and modify current standards for care. Knowledge gained from this proposal, the first to rigorously examine the response to metformin in T1D, will provide novel information about the role of IR in early CVD development in T1D and focus future interventions. We are uniquely poised to address the nature and consequences of IR in T1D youth. Our novel imaging techniques that can noninvasively assess mitochondrial dysfunction (MitoD) in youth with exercise. Our advanced echocardiography indices and are validating noninvasive vascular biomarkers to identify early progressors that may benefit from more intensive interventions. Our expertise in 3-stage hyperinsulinemic clamps with isotopes in T1D youth is also a unique strength. In parallel with this proposal in T1D youth, we are also performing similar studies of IR, on control, obese and T2D youth, which will enable novel comparisons to the T1D youth studied in this protocol.

